#### **3.4 Exclusion Criteria for Arm A and Arm B:**

- 3.4.1 Patients who have had systemic anti-tumor therapy (such as chemotherapy, biologic modifiers or antiangiogenic therapy) within 4 weeks (6 weeks if nitrosourea or mitomycin chemotherapy) prior to study entry.
- 3.4.2 Patients who have had external beam radiation therapy within 1 week or if the adverse events associated with radiation are not resolved to grade 1 or less prior to study entry.
- 3.4.3 Prior therapy with sorafenib (BAY 43-9006), ZD 6474 or AMG-706.
- 3.4.4 Patients currently receiving any other tumor-specific therapy for thyroid cancer or investigational therapy. Patients receiving adjuvant hormonal therapy for a second primary (such as breast cancer or prostate cancer) are allowed to participate as far as there are no known drug interactions.
- 3.4.5 History of allergic reactions attributed to compounds of similar chemical or biologic composition to sorafenib (BAY 43-9006).
- 3.4.6 Patients unable to swallow sorafenib tablets. (e.g. Any condition that impairs patient's ability to swallow pills)
- 3.4.7 Uncontrolled intercurrent illness including, but not limited to, ongoing or active infection, uncontrolled hypertension, or psychiatric illness/social situations that would limit

compliance with study requirements.

- 3.4.8 Patients with any evidence of a bleeding diathesis.
- 3.4.9 Patients actively receiving anticoagulation with therapeutic intent. Prophylactic anticoagulation (i.e. low dose warfarin) or venous or arterial access devices is allowed provided that the PT, INR or PTT are normal.
- 3.4.10 Pregnant women or women who are breast-feeding are excluded from this study because sorafenib (BAY 43-9006) is an investigational agent and teratogenicity has not been evaluated yet. Because there is an unknown but potential risk for adverse events in nursing infants secondary to treatment of the mother with sorafenib (BAY 43-9006), breastfeeding should be discontinued if the mother is treated with sorafenib (BAY 43-9006).
- 3.4.11 HIV-positive patients receiving combination anti-retroviral therapy because of possible pharmacokinetic interactions with sorafenib (BAY 43-9006). Patients with immune deficiency are at increased risk of lethal infections when treated with marrow-suppressive therapy.

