**Version 2.7, November 16, 2015**

Adverse Events with Possible Relationship to Sorafenib (BAY 43-9006) (CTCAE 4.0 Term) [n= 2571]			Specific Protocol Exceptions to Expedited Reporting (SPEER)
Likely (>20%)	Less Likely (<=20%)	Rare but Serious (<3%)	
BLOOD AND LYMPHATIC SYSTEM DISORDERS			
Anemia			Anemia (Gr 3)
CARDIAC DISORDERS			
		Acute coronary syndrome	
	Chest pain - cardiac		
		Heart failure	
		Left ventricular systolic dysfunction	
		Myocardial infarction	
GASTROINTESTINAL DISORDERS			
Abdominal pain			Abdominal pain (Gr 3)
	Ascites		
	Constipation		Constipation (Gr 2)
Diarrhea			Diarrhea (Gr 3)
	Gastrointestinal hemorrhage 		Gastrointestinal hemorrhage (Gr 3)
		Gastrointestinal perforation 	
	Mucositis oral		
Nausea			Nausea (Gr 3)
	Vomiting		Vomiting (Gr 3)
GENERAL DISORDERS AND ADMINISTRATION SITE CONDITIONS			
	Edema limbs		
Fatigue			Fatigue (Gr 3)
	Fever		Fever (Gr 2)
HEPATOBILIARY DISORDERS			
		Hepatic Failure	
IMMUNE SYSTEM DISORDERS			
		Anaphylaxis	
INFECTIONS AND INFESTATIONS			
	Infection 		
INVESTIGATIONS			

Adverse Events with Possible Relationship to Sorafenib (BAY 43-9006) (CTCAE 4.0 Term) [n= 2571]			Specific Protocol Exceptions to Expedited Reporting (SPEER)
Likely (>20%)	Less Likely (<=20%)	Rare but Serious (<3%)	
	Activated partial thromboplastin time prolonged		Activated partial thromboplastin time prolonged (Gr 2)
Alanine aminotransferase increased			Alanine aminotransferase increased (Gr 3)
Alkaline phosphatase increased			Alkaline phosphatase increased (Gr 3)
Aspartate aminotransferase increased			Aspartate aminotransferase increased (Gr 3)
Blood bilirubin increased			Blood bilirubin increased (Gr 3)
Creatinine increased			Creatinine increased (Gr 3)
	GGT increased	Electrocardiogram QT corrected interval prolonged	
INR increased			INR increased (Gr 3)
	Investigations - Other (bicarbonate-serum low)		
Lipase increased			Lipase increased (Gr 3)
Lymphocyte count decreased			Lymphocyte count decreased (Gr 3)
	Neutrophil count decreased		Neutrophil count decreased (Gr 4)
Platelet count decreased			Platelet count decreased (Gr 4)
Serum amylase increased			Serum amylase increased (Gr 3)
Weight loss			Weight loss (Gr 2)
White blood cell decreased			White blood cell decreased (Gr 4)

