METABOLISM AND NUTRITION DISORDERS			
Anorexia			Anorexia (Gr 3)
Hyperglycemia	Hypercalcemia		Hyperglycemia (Gr 3)
	Hyperkalemia		Hyperkalemia (Gr 3)
	Hypernatremia		
Hypoalbuminemia			Hypoalbuminemia (Gr 3)

Adverse Events with Possible Relationship to Sorafenib (BAY 43-9006) (CTCAE 4.0 Term) [n= 2571]			Specific Protocol Exceptions to Expedited Reporting (SPEER)
Likely (>20%)	Less Likely (<=20%)	Rare but Serious (<3%)	
Hypocalcemia			Hypocalcemia (Gr 3)
	Hypoglycemia		Hypoglycemia (Gr 2)
	Hypokalemia		Hypokalemia (Gr 3)
Hyponatremia			Hyponatremia (Gr 3)
Hypophosphatemia			Hypophosphatemia (Gr 3)
MUSCULOSKELETAL AND CONNECTIVE TISSUE DISORDERS			
	Arthralgia		Arthralgia (Gr 3)
	Back pain		Back pain (Gr 3)
	Bone pain		
	Musculoskeletal and connective tissue disorder - Other (muscle spasm)		
	Myalgia		
	Pain in extremity		Pain in extremity (Gr 3)
NEOPLASMS BENIGN, MALIGNANT AND UNSPECIFIED (INCL CYSTS AND POLYPS)			
	Treatment related secondary malignancy		
NERVOUS SYSTEM DISORDERS			
	Dizziness		
	Headache		Headache (Gr 3)
		Intracranial hemorrhage	
		Reversible posterior leukoencephalopathy syndrome	
PSYCHIATRIC DISORDERS			
	Insomnia		
RENAL AND URINARY DISORDERS			
	Acute kidney injury		
RESPIRATORY, THORACIC AND MEDIASTINAL DISORDERS			
	Cough		Cough (Gr 2)
	Dyspnea		Dyspnea (Gr 3)
	Respiratory hemorrhage 		

Adverse Events with Possible Relationship to Sorafenib (BAY 43-9006) (CTCAE 4.0 Term) [n= 2571]			Specific Protocol Exceptions to Expedited Reporting (SPEER)
Likely (>20%)	Less Likely (<=20%)	Rare but Serious (<3%)	
	Voice alteration		
SKIN AND SUBCUTANEOUS TISSUE DISORDERS			
Alopecia			Alopecia (Gr 2)
	Dry skin		Dry skin (Gr 2)
Palmar-plantar erythrodysesthesia syndrome		Erythema multiforme	Palmar-plantar erythrodysesthesia syndrome (Gr 3)
	Pruritus		Pruritus (Gr 3)
Rash maculo-papular			Rash maculo-papular (Gr 3)
		Stevens-Johnson syndrome Toxic epidermal necrolysis	
VASCULAR DISORDERS			
	Hypertension		Hypertension (Gr 3)
		Thromboembolic event	

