**Biopsies will not be performed under one of the following circumstances:**

- Investigator's disapproval
- Funding for the biopsies is not sufficiently available
- Patient refuses to undergo the procedure.

**In such cases biopsies may be performed pre-treatment (within 4 weeks prior to starting treatment) and at 8 wks on treatment. Post-treatment (within 4 wks after last dose of treatment) biopsies in these patients may be performed per investigator's discretion.** Please note that the CT or MRI, DCE-MRI, and PET scan that might need to be done at these time points should be done prior to doing biopsy procedure. No specific time interval is necessary between these imaging studies and biopsy.

**Sample collection and processing:** Fine needle aspiration (FNA) biopsies (using 18-21 gauge needle) of the tumor (ie: either cervical lymph nodes or bulky bony or lung or liver metastasis) will be performed under imaging guidance or blindly depending on the location and size of the tumor.

Fine needle aspirated material will be collected in the tubes containing RPMI media. No direct smears slides will be made from FNA. Using Autocyte PREP system standard protocol, slides will be prepared using CytoRich® Red (Tripath Imaging) cytological preservative. The actual slides used will be PLUS slides; as these are precoated that facilitates the cells staying on the slides during processing. At least 8 unstained slides will be prepared using the standard protocol. Two slides will be stained with PapStain for cytologic diagnosis so that we verify that tumor was indeed present in the FNA specimen.

**Principle of Autocyte PREP system:** The AutoCytE PREP System converts a liquid suspension of a cell sample into discretely stained, homogenous thin-layer of cells while maintaining diagnostic cell clusters. The process includes cell preservation, randomization, enrichment of diagnostic material, automated pipetting, sedimentation, and discrete staining portions of the process. The AutoCytE PREP presents a wellpreserved population of stained cells present within a 13mm diameter circle. Using this system, we have been able to perform immunohistochemistry studies on specimens prepared from FNA material in our ongoing CTEP- sponsored phase II trial (NCI 6609).

All stained and unstained slides will be shipped to [name] at the OSU (see [Appendix B](#) for shipping instructions) who then will transfer batched specimen to [name] laboratory.

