## 8 STUDY CALENDAR

	Pre-therapy a	Course I (subsequent courses as course I b )		Off-therapy c
		Week 4 b	Week 8	
Sorafenib (BAY 43-9006) d				
Patient diaries		X	X	X
History/Physical Exam	X	X	X	X
Vital signs/Weight	X	X	X	X
Blood pressure monitoring	Once a week till stable or at least for the first 4 weeks.			X
Adverse Event Evaluation		X	X	X
CBC w/diff, platelets	X	X	X	X
Serum chemistry e	X e	X e	X e	X e
Serum β-HCG f	X f			
CT or MRI scan of neck/chest/abdomen g	X g		X g	X g
Serum Calcitonin and CEA	X		X	X
Following tests may be done in selected group of patients ONLY. See Sec7.0 for the details.				
10-mLblood for procurement of serum ( Section 7.1 )	X			
PET scan ( Section 7.2 ) h	X		X	X
DCE-MRI scan ( Section 7.3 )	X		X	X i
20-mLblood for plasma and PBMCs ( Section 7.4 )	X			
FNA biopsy of the tumor ( Section 7.5 )	X k		X k	X j
Paraffin tumor tissue block ( Section 7.6 )	X			
RET genotyping to clinical lab ( Section 7.6 )	X			
a: Pre-therapy evaluations are to be conducted within 10 days prior to administration of sorafenib (BAY 43-9006) except imaging studies, research blood draws, and tumor biopsies that should be done within 4 weeks prior to the start of therapy.				
b: Week 4 evaluations may be done at local doctor's office. However, AE eval must be by research staff via phone interview with the patient and principal investigator must sign off on adverse event data forms within 36 hours of the phone interview.				
c: Off-therapy evaluations are to be conducted within 4 weeks after last dose of sorafenib (BAY 43-9006) treatment. Serum calcitonin and CEA, CT/MRI scans will be optional if a patient received sorafenib (BAY 43-9006) for ≤4 weeks.				
d: Oral sorafenib (BAY 43-9006) will be given with 250 ml (about 8 ounces) of water at the dose of 400 mg BID.				
e: Sodium, Potassium, Chloride, Bicarbonate, Creatinine, BUN, Glucose, Phosphorus, Total protein, Albumin, Total bilirubin, S GOT (AST), SGPT (ALT), Alkaline phosphatase, LDH.				
f: Pregnancy test (sensitivity of at least 50 mIU/mL) will be performed for all women of childbearing potential before beginning sorafenib (BAY 43-9006).				

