We will consider sorafenib (BAY 43-9006) to be ineffective or uninteresting if the true response [PR+CR using unidimensional RECIST/WHO response criteria] probability is less than 10% ( $p_0$ ). We will also assume that the regimen is worthy of further study if the true response probability or target response rate is 30% or greater ( $p_1$ ). These figures result in a two-stage design of 16 and 25 patients, with an alpha of 0.10 and beta of 0.10. If one or no responses are seen in the first 16 response-evaluable patients, the study is terminated early and this regimen is deemed ineffective for this patient population. If two or more patients respond in the first 16, an additional 9 patients are treated for a total of 25. If 5 or more patients respond of the 25, we will recommend that the regimen be studied further. If 25 patients are treated, we will be able to estimate the frequency of response with a 95% confidence interval of not greater than 19.6%.

Similarly, the 25 patients in each of Arms A and B will allow us to estimate the probability of a specific toxicity to within  $\pm 19.6\%$  in each cohort. Any toxicity occurring with at least a 10% probability has a 92.8% chance of being seen at least once in 25 toxicity-evaluable patients.

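### Four laboratory toxicities that the protocol lists as likely (>20%) have no scheduled test, so the section 11.1 detection and precision statements do not apply to them

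*Combined protocol and SAP*

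**What the plan says.** Assessing toxicity is secondary objective 1.2.1. Section 11.4.1 counts every patient as evaluable for toxicity from the first dose.

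Section 11.1 gives two statements about what 25 patients per arm can show. The first is that a specific toxicity can be estimated to within ±19.6%. The second reads: "Any toxicity occurring with at least a 10% probability has a 92.8% chance of being seen at least once" in 25 toxicity-evaluable patients.

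The calendar in section 8 schedules a CBC and serum chemistry before therapy, at weeks 4 and 8, and off therapy. Footnote e defines the chemistry. It opens "Sodium, Potassium, Chloride, Bicarbonate, Creatinine, BUN, Glucose, Phosphorus, Total protein, Albumin, Total bilirubin" and adds AST, ALT, alkaline phosphatase and LDH. Nothing in it marks the list as a set of examples. The other scheduled bloods are a pre-therapy pregnancy test, the tumor markers, and research or genotyping samples.

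The risk list in section 6.2, based on 2571 patients, places these entries against its Likely (>20%) column (closing brackets omitted): "INR increased (Gr 3", "Lipase increased (Gr 3", "Serum amylase increased (Gr 3" and "Hypocalcemia (Gr 3". The grade shown is each event's threshold for exception from expedited reporting.

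Exclusion 3.4.9 allows prophylactic anticoagulation "provided that the PT, INR or PTT are normal". Neither the laboratory list in 3.3.7 nor the calendar contains a coagulation test.

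**The concern.** These four events are defined by a laboratory value. The scheduled history, physical examination and adverse event review cannot stand in for an assay. If a site follows the calendar exactly, it obtains no calcium, lipase, amylase or INR result.

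Any results that do exist would come from tests ordered for a clinical reason. That sample is selective, and a patient tested on treatment may have no pre-treatment value with which to separate a new abnormality from an old one. A count of events over all treated patients would then probably understate incidence. A count over tested patients only would describe an unrepresentative subgroup.

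Section 11.1 makes no such distinction. Its statements are worded for any toxicity, but the arithmetic behind them needs every evaluable patient to be measured. The reporting thresholds for the four events likewise cannot be applied consistently without values.

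**Working it through.** **Coverage of the Likely column.** The laboratory terms in the Likely (>20%) column of section 6.2, set against the calendar:

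| Scheduled test | Likely laboratory events covered | Count |
|---|---|---|
| CBC with differential and platelets | anemia; lymphocytes, platelets and white cells decreased | 4 |
| Footnote e chemistry | ALT, AST, alkaline phosphatase, bilirubin and creatinine increased; hyperglycemia; hypoalbuminemia; hyponatremia; hypophosphatemia | 9 |
| None | INR, lipase and serum amylase increased; hypocalcemia | 4 |

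The total is 4 + 9 + 4 = 17. Thirteen events are covered and four are not (4/17 = 24%). In the Less Likely column, prolonged aPTT, raised GGT and hypercalcemia also have no scheduled test.

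**The plan's own figures.** Both reproduce:

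- Detection: 1 − (1 − 0.10)^25 = 1 − 0.9^25 = 0.928.
- Half-width at the worst case of 50%: 1.96 × √(0.5 × 0.5 / 25) = 0.196.

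In both, 25 is the number of patients in whom the event would be recorded if it occurred.

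**Effect of incomplete testing.** Let p be the true rate and f the share of patients tested outside the calendar. If testing is unrelated to the event, the chance of seeing it at least once in 25 patients is 1 − (1 − p·f)^25. The documents give no value for f, so a range is assumed:

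| Share tested, f | p = 10% | p = 20% |
|---|---|---|
| 1.00 | 92.8% | 99.6% |
| 0.50 | 72.3% | 92.8% |
| 0.25 | 46.9% | 72.3% |
| 0.10 | 22.2% | 39.7% |
| 0 | 0% | 0% |

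For example, p = 20% and f = 0.25 give 1 − (1 − 0.05)^25 = 0.723. If an arm stops at 16 patients, full testing gives 81.5% at p = 10% and 97.2% at p = 20%.

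Precision falls in the same way. With f = 0.25, about 25 × 0.25 = 6.25 patients contribute, and the worst-case half-width becomes 1.96 × √(0.25 / 6.25) = 0.392, twice the stated figure.

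The formula does not model selection. Testing prompted by symptoms could make detection higher than shown, but it would bias the estimated rate.

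**The case against.** The strongest reply is that the calendar sets a minimum. Nothing forbids further tests, adverse events are reviewed at every scheduled visit, and the monthly flowsheets in section 10.3.3.1 collect laboratory values and toxicities without limiting them to footnote e. This stands against one tempting inference, that the trial cannot observe these events or would report rates near zero. The documents show only that no measurement is scheduled, and they do not say that untested patients would be counted as event-free. Zero detection is one end of a range that depends on an unstated f.

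A second reply is that the risk list is not a monitoring schedule. Its frequencies are pooled over 2571 patients, with no split by grade and no indication that they describe patients with this disease. This also stands. The 20% rate used above is an assumption taken from the column heading, not a prediction for these arms.

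Third, it is tempting to call the 92.8% statement false. It is a correct binomial calculation. What it lacks is the condition that all patients are measured.

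Fourth, a reader might infer that exclusion 3.4.9 has no test behind it. The criterion itself requires normal results in the patients it covers, and section 10.3.2 requires an eligibility checklist and pre-therapy laboratory reports before registration. Only a calendar entry and a time window are missing.

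Finally, the missing INR could be linked to the week 8 needle biopsies in section 7.5. The documents do not support making that a finding. The biopsies are optional, cervical nodes are among the possible sites, the investigator may decline them, and no section makes them depend on a coagulation value.

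None of these replies supplies a scheduled measurement or a common baseline for the four events.

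**Conclusion.** The concern holds as a gap in ascertainment for a secondary objective. Four of 17 likely laboratory events have no scheduled test. Their incidence would rest on selective testing and would probably be under-reported, and the two precision statements in section 11.1 do not apply to them.

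The size depends on the share of patients tested off-calendar, which the documents do not give. For a true 20% event in 25 patients, detection runs from 99.6% with full testing down to 0% with none. The omission itself is certain from the text. The degree of under-reporting is not, because it assumes a true rate and an off-calendar testing pattern.

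The coagulation point is a smaller matter of reconciliation: 3.4.9 calls for a check that the calendar and 3.3.7 do not place. The response endpoint and the two-stage design are untouched. The change should be made, but nothing in the primary analysis depends on it.

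**What to change.** 1. In footnote e of section 8, add calcium (read with the albumin already collected), lipase and amylase at the existing draws.
2. In section 11.1, limit the 92.8% and ±19.6% statements to toxicities that the calendar assesses. That leaves INR outside them unless the sponsor also schedules it on treatment.
3. Reconcile exclusion 3.4.9 with the calendar by giving its PT/INR/PTT check a pre-therapy entry and a time window for the patients it covers.

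What follows from an abnormal value is for the sponsor to decide.

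The cost is a calendar amendment and modest assay expense. Part of that expense falls on local offices, because footnote b lets week 4 evaluations be done there. More low-grade laboratory events will also have to be recorded. The change to section 11.1 is wording only.

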## 9 MEASUREMENT OF EFFECT

For the purposes of this study, patients should be reevaluated for response every 16 weeks. Confirmatory scans should also be obtained 4 weeks following initial documentation of objective response.

### 9.1 Definitions

Response and progression will be evaluated in this study using the new international criteria proposed by the Response Evaluation Criteria in Solid Tumors (RECIST) Committee (Therasse *et al.*, 2000). Changes in only the largest diameter (unidimensional measurement) of the tumor lesions are used in the RECIST criteria. **Note:** Lesions are either measurable or non-measurable using the criteria provided below. The term 'evaluable' in reference to measurability will not be used because it does not provide additional meaning or accuracy.

#### 9.1.1 Measurable disease

Measurable lesions are defined as those that can be accurately measured in at least one dimension (longest diameter to be recorded) as  $\geq 20$  mm with conventional techniques (CT, MRI, x-ray) or as  $\geq 10$  mm with spiral CT scan or MRI performed with following technique:

MRI images acquired in at least two imaging planes (such as axial and coronal) that give 'in-plane' resolution of at least 2.5 mm.

All tumor measurements must be recorded in millimeters (or decimal fractions of centimeters).

Note: Tumor lesions that are situated in a previously irradiated area will not be considered measurable unless the lesion in irradiated area shows progression.

#### 9.1.2 Non-measurable disease

All other lesions (or sites of disease), including small lesions (longest diameter  $<20$  mm with conventional techniques or  $<10$  mm using spiral CT scan or MRI with 'in-plane resolution of 2.5 mm'), are considered non-measurable disease. Bone lesions, leptomeningeal disease, ascites, pleural/pericardial effusions, lymphangitis cutis/pulmonis, inflammatory breast disease, abdominal masses (not followed by CT or MRI), and cystic lesions are all non-measurable.

#### 9.1.3 Target lesions

All measurable lesions up to a maximum of five lesions per organ and 10 lesions in total, representative of all involved organs, should be identified as **target lesions** and recorded and measured at baseline. Target lesions should be selected on the basis of their size (lesions with the longest diameter) and their suitability for accurate repeated measurements (either by imaging techniques or clinically). A sum of the longest diameter (LD) for all target lesions will be calculated and reported as the baseline sum LD. The baseline sum LD will be used as reference by which to characterize the objective tumor response.

#### 9.1.4 Non-target lesions

All other lesions (or sites of disease) should be identified as **non-target lesions** and should also be recorded at baseline. Non-target lesions include measurable lesions that exceed the maximum numbers per organ or total of all involved organs as well as non-measurable lesions. Measurements of these lesions are not required, but the presence or absence of each should be noted throughout follow-up.

### 9.2 Guidelines for Evaluation of Measurable Disease

All measurements should be taken and recorded in metric notation using a ruler or calipers. All baseline evaluations should be performed as closely as possible to the beginning of treatment and never more than 4 weeks before the beginning of the treatment.

Note: Tumor lesions that are situated in a previously irradiated area will not be considered measurable unless the lesion in irradiated area shows progression.

The same method of assessment and the same technique should be used to characterize each identified and reported lesion at baseline and during follow-up. Imaging-based evaluation is preferred to evaluation by clinical examination when both methods have been used to assess the anti-tumor effect of a treatment.

**Clinical lesions.** Clinical lesions will only be considered measurable when they are superficial (e.g., skin nodules and palpable lymph nodes). In the case of skin lesions, documentation by color photography, including a ruler to estimate the size of the lesion, is recommended.

**Chest x-ray.** Lesions on chest x-ray are acceptable as measurable lesions when they are clearly defined and surrounded by aerated lung. However, CT is preferable.

**Conventional CT and MRI.** These techniques should be performed with cuts of 10 mm or less in slice thickness contiguously. Spiral CT should be performed using a 5 mm contiguous reconstruction algorithm. This applies to tumors of the chest, abdomen, and pelvis.

**Ultrasound (US).** When the primary endpoint of the study is objective response evaluation, US should not be used to measure tumor lesions. It is, however, a possible alternative to clinical measurements of superficial palpable lymph nodes, subcutaneous lesions, and thyroid nodules. US might also be useful to confirm the complete disappearance of superficial lesions usually assessed by clinical examination.

**Endoscopy, Laparoscopy.** The utilization of these techniques for objective tumor evaluation has not yet been fully and widely validated. Their uses in this specific context require sophisticated equipment and a high level of expertise that may only be available in some centers. Therefore, the utilization of such techniques for objective tumor response should be restricted to validation purposes in reference centers. However, such techniques may be useful to confirm complete pathological response when biopsies are obtained.

**Tumor markers.** Tumor markers alone cannot be used to assess response. If markers are

initially above the upper normal limit, they must normalize for a patient to be considered in complete clinical response.

**Cytology, Histology.** These techniques can be used to differentiate between partial responses (PR) and complete responses (CR) in rare cases (e.g., residual lesions in tumor types, such as germ cell tumors, where known residual benign tumors can remain).

The cytological confirmation of the neoplastic origin of any effusion that appears or worsens during treatment when the measurable tumor has met criteria for response or stable disease is mandatory to differentiate between response or stable disease (an effusion may be a side effect of the treatment) and progressive disease.

